*Conceptual Framework.* We predict the Partnership intervention will improve school culture so that staff and students are more knowledgeable about mental health, less concerned about stigma, and more proactive in identifying students in need and connecting them to more intensive Tier 2 or Tier 3 services; more students/families receive Tier 2 and 3 services and receive them in a more timely manner; students and families are more invested in services, empowered to influence treatment directions, experience greater therapeutic alliance with SBH staff, and receive a higher dose of evidence-based services; and, impacts of evidence-based services are amplified based on greater knowledge of mental health. These factors will be associated with better performance on measures of social, EB, and academic functioning than students in the Wellness Group alone.

*Engagement Plan.* The engagement plan has been informed by lessons learned from the recent PCORI Eugene Washington Engagement award, and reviewer feedback from the prior application. The SAB has actively guided our work and this resubmission, with some members providing input since 2015, and new members (i.e., educators, additional family members, payers) added based on PCORI guidance. The SAB has 13 members in SC and 10 in MD (23 total) and includes: patients/caregivers (some of whom are end users at study schools), educators, mental health/community partners, public and private funders, and community partners (see Tables 3 and 4 in Appendix for a full listing of members by site). Please note that the SAB is representative of study sites in relation to racial/ethnic/cultural background of students. The SAB will collaborate at multiple levels, as a full 23-member board, within SC and MD, and in three subgroups of patients/caregivers, educators, and mental health/community partners. The SAB subgroups will convene in bi-monthly conference calls for one hour to provide input and feedback in all three domains of the PCORI engagement rubric: Planning, Conduct and Dissemination. Each SAB member will be compensated \$50 per hour for their time spent on the calls, as well as the time they spend reviewing materials offline (estimated at 6 hours annually). Additionally, the SAB will meet in person once annually, to engage in more comprehensive discussion of

PRINCIPAL INVESTIGATOR: [name]

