### **Study Design.**

*Measures and Measurement Plan.* All measures chosen for use in the study are in the public domain and have strong psychometric properties (e.g., internal consistency, test-retest reliability, concurrent validity). There will be two streams of data collection involving students. The first will be data collected to reflect school-wide impacts of the Partnership Condition focusing on academic record variables of students' grades, attendance, lateness and discipline referrals (including office discipline referrals and suspensions), and school climate. School-wide academic record data will be collected for all students and de-identified to the research team (it is considerably less burdensome for schools to share deidentified data for all students than to share for a sample of them). School climate data will be collected for a sample of about 60 students (3 randomly selected classrooms), and 25-40 staff (requesting all staff complete) at each of the 22 schools. School-wide academic record data will be collected once annually for the academic year prior to study start (2018-19), and will be collected each year for the three years of intervention vs. comparison, per procedures that we are replicating based on the current NIJ-funded RCT. Selected students and staff will complete the School Climate Survey (SCS) a free, online school climate survey from the US Department of Education (<https://safesupportivelearning.ed.gov/edscls>). The SCS is available as a web-based platform and includes a suite of school climate surveys for students, instructional staff, and non-instructional staff. Staff and students will be asked to

PRINCIPAL INVESTIGATOR: [name]

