*Aim 2: Evaluate the impact of the Partnership enhancements on students' social, emotional/behavioral (EB), and academic outcomes.* For this primary aim, there will be two sub-aims: Aim 2a will evaluate the impact of the Partnership enhancements on school-wide academic record variables of grades, attendance, lateness and discipline referrals. Aim 2b will focus on students receiving Tier 3 services and will assess their social and emotional/behavioral (EB) functioning. To assess social functioning, the Child and Adolescent Social and Adaptive Functioning Scale (51) will be completed by students. The CASAFS includes 24 items measuring students' functioning in four key social roles: school performance, peer relations, family relations, and home duties/self-care. Additionally, both "internalizing" EB problems, which include problems of depression, anxiety and exposure to trauma, and "externalizing" EB problems, which include conduct and attention problems, will be measured for students receiving Tier 3 services. Student EB functioning will be measured by parent and student report forms of the Brief Problem Checklist (52), a 12-item questionnaire that measures externalizing and internalizing problems. Derived from the comprehensive Child Behavior Checklist (53), it is designed for repeated periodic assessment of clinical progress, yielding both an internalizing and externalizing subscale (52). Please note that academic variables collected above school-wide for stream 1 data collection, will also be used for stream 2 data collection for students receiving Tier 3 services. Changes in the above variables will be assessed for students for the academic quarter before receiving mental health services and the academic quarter after services have been completed.

*Additional Measures.* In addition to measures directly reflecting study aims, secondary aims will be addressed by measures reflecting the potential impact of the two Partnership enhancements will be collected at the same time intervals for students receiving Tier 3 services. For the enhancement focused on mental health education and stigma reduction, students will complete The Guide Curriculum Assessment (GCA) reviewed previously (43,44). The GCA includes subscales assessing Mental Health Literacy in three dimensions: Mental Health Knowledge (MHK; 28 items),

PRINCIPAL INVESTIGATOR: [name]

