The second avenue of recruitment will be for students receiving Tier 3 treatment services. These students/parents will be consented using electronic consent (e-consent) in REDCap, with the consent form appended at the beginning of the survey. Participants and their parents will be required to go through the informed consent process and digitally sign the consent form using a mobile tablet device before proceeding into the survey questionnaire. MUSC has successfully piloted e-consent in REDCap with other IRB approved research studies. Given challenges with parents' ability to attend meetings at the school to complete the enrollment process, the study team developed protocol to allow for consent to be gained via phone and intake to be completed remotely via phone or computer. This flexibility allows enrollment to continue, and not be hampered by potential transportation or financial constraints that may otherwise prevent low-income families from participating. Additionally, as result of the COVID-19 crisis, procedures were developed to allow students to assent into the study via telephone or video conference. Students and parents may provide assent/consent via phone, after viewing consent materials and having the opportunity to ask questions of the clinician. Intake assessments can be completed verbally (via phone or video conference) or a link to complete surveys online may be sent via email or directly through the REDCap program by the clinician or research manager.

PRINCIPAL INVESTIGATOR: [name]

Based on current prevalence data, twenty percent (2,14) of students are expected to present with mental health challenges (n= 4,000). Of these students, based on the experience in similar studies the research team estimates that 30% will consent to participate representing the recruitment goal of 1,225 students by the end of the 2022-23 academic year. The rate of recruitment will be higher initially due to enrollment of students currently receiving services, however, over the course of the study an average of 35 students per month (during the academic year only, or four years times 9 months for 36 months total) will be enrolled. Note: significant changes to enrollment targets have been made during this project largely related to the unanticipated and unprecedented impact of the COVID-19 pandemic which temporarily closed school buildings and changed mental health care services starting in March 2020.

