There are essentially six classes of student participants, with groups based on grade level at the start of the intervention vs. comparison (IvC) period of the study, which begins in the 2019-20 school year. There is a four-year IvC period, 2019-20, 2020-21, 2021-22, and 2022-23. Group A will be in the 6th grade in 2019-20, with students experiencing 1-3 years of services in this time interval. These students could have received services in 6th, 7th and/or 8th grades during the IvC period. Group B will be in the 7th grade in 2019-20, with students experiencing 1-2 years of services in this time interval. These students could have received services in 7th and/or 8th grades during the IvC period. Group C will be in the 8th grade in 2019-20, with students experiencing 1 year of services in this time interval. Group D will enter the study in 6th grade in 2020-21. Group E will enter the study in 6th grade in 2021-22. Group F will enter the study in 2022-2023 while in 6th grade.

*Identifying eligible participants.* Participants already receiving treatment and those newly referred for services will be eligible to participate and recruited by their SBH clinician. Throughout the implementation phase (years 1-4) each school will use their existing referral process to identify students in need of treatment which will be followed up and confirmed by the SBH clinician prior to enrolling them in the study.

*Overcoming barriers to enrollment.* In addition to our successful experiences with the opt-out procedure to be used for stream 1 data collection, both mental health centers have participated in extensive and similar research with the investigators leading this study. The SAB will provide input on the development of consent materials, and methods of communication, making sure that they are appealing. The process of utilizing e-consent will be convenient and streamlined for Tier 3 participants. Additionally, participant incentives are proposed, in the amount of \$20 per parent assessment battery, and a token of appreciation for each student assessment battery to incentivize participation.

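### The Tier 3 academic change score has no pre-service quarter for students who start services in quarter 1 of 6th grade or whose services began before the records window, and the plan gives no rule for them

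*Combined protocol and SAP*

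**What the plan says.** The Aim 2 paragraph under Measures and Measurement Plan defines the academic outcome for Tier 3 students: "Changes in the above variables will be assessed for students for the academic quarter before receiving mental health services". The comparison is with the first quarter following the end of services. The paragraph names one data source: "academic variables collected above school-wide for stream 1 data collection, will also be used for stream 2 data collection".

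The opening of Measures and Measurement Plan describes those records: "School-wide academic record data will be collected once annually for the academic year prior to study start (2018-19"), after which they "will be collected each year for the three years of intervention vs. comparison". They cover all students of the participating schools, which are middle schools. Protection of Human Subjects limits participation to grades 6 to 8.

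On who can enrol, Identifying eligible participants says: "Participants already receiving treatment and those newly referred for services will be eligible to participate". The Recruitment Plan adds: "The rate of recruitment will be higher initially due to enrollment of students currently receiving services". It gives no number for this group.

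The Analytic Plan's section on model modifications for Tier 3 makes the difference score the dependent variable. The general missing-data method is full information maximum likelihood (FIML). No section provides for elementary-school records, records before 2018-19, a substitute baseline quarter, or a rule for a missing pre-service quarter.

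**The concern.** A difference score needs both of its parts. If the quarter before services lies outside the records collected, the student has no outcome in this analysis, whatever happens later. The students affected are not a random subset. They are those served earliest in 6th grade and those with the longest treatment histories.

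Tier 3 academic change belongs to Aim 2, which the plan calls primary. The Conceptual Framework also predicts that under Partnership "more students/families receive Tier 2 and 3 services and receive them in a more timely manner". If earlier access moved some starts into quarter 1 of 6th grade, the students excluded could differ between arms. With no count by arm, a reader of the results could not tell.

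**Working it through.** This point disputes no stated figure. The check asks whether the preceding quarter falls inside the described records.

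**Inputs.** Pre-service window: the quarter before services (Aim 2 paragraph). Records: study schools, grades 6 to 8, from 2018-19 (Measures and Measurement Plan; Protection of Human Subjects). Intervention: 2019-20 to 2022-23 (Study Population and Setting). Assumed: four quarters per school year, and all 22 schools supply records for the whole window.

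**New starters.** There are 3 grades × 4 quarters × 4 years = 48 possible start cells.
- Records run through 2022-23: only quarter 1 starts in 6th grade lack the preceding quarter, because it was in 5th grade. That is one cell per year, 4/48 = 8.3% if starts are spread evenly.
- Records stop after three intervention years, as Measures and Measurement Plan reads: the quarter 2 to 4 starts of 2022-23 are lost as well, 3 quarters × 3 grades = 9 cells. The total is (4 + 9)/48 = 27.1%.

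**Already in treatment at the start of 2019-20.**

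| Grade in 2019-20 | Services began in quarters 2-4 of 2018-19 | Services began in quarter 1 of 2018-19 or earlier |
|---|---|---|
| 6th | no pre-quarter (elementary school) | no pre-quarter |
| 7th | pre-quarter available | no pre-quarter |
| 8th | pre-quarter available | no pre-quarter |

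The 2018-19 baseline year therefore covers part of this group. How large a part depends on start dates that the documents do not give. As an illustration, spread starts evenly over the previous 2, 4 or 8 quarters. Then 0/2 = 0%, 1/4 = 25% or 5/8 = 62.5% of 7th and 8th graders lack the quarter. With equal numbers per grade and every 6th grader uncovered, the overall share is (100 + 0 + 0)/3 = 33%, (100 + 25 + 25)/3 = 50% or (100 + 62.5 + 62.5)/3 = 75%. Students who enrol in later years while in treatment lack it only if services began in elementary school, in quarter 1 of 6th grade, or before quarter 2 of 2018-19.

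**FIML.** When the single outcome is post minus pre and pre was never collected, the outcome itself is missing. The student adds nothing to the likelihood unless the post value is modelled separately or auxiliary variables are added. The plan specifies neither.

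**Precision.** Power considerations states a minimum detectable effect size (MDES) of .29 for N = 1225, J = 22 schools and 30% of variance explained. It gives no intraclass correlation (ICC), so the figure can only be matched. The formula, with n = N/J, is MDES = M × √[ICC(1−R²)/(0.25J) + (1−ICC)(1−R²)/(0.25Jn)]. With M = 2.954 (two-sided 5%, 80% power, 19 degrees of freedom), R² = .30 at both levels and n = 55.7, an ICC of .0588 gives 2.954 × √(.00748 + .00215) = .290. Losing scores evenly across schools inflates only the second term:

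| Scores lost | MDES |
|---|---|
| 8.3% | .293 |
| 20% | .298 |
| 33% | .306 |
| 50% | .321 |

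With 22 schools the between-school term dominates, so the loss of precision is modest.

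**The case against.** Several points on the other side stand.

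- Scope is narrow. The social functioning scale (CASAFS) and the Brief Problem Checklist are collected at intake, and Aim 2a is school-wide. Neither depends on a pre-service quarter.
- Annual collection is not in itself a conflict with a quarterly outcome. It describes how often records are transferred, and the Aim 2 paragraph itself calls for quarter values.
- The plan does not rule out obtaining earlier records. These students are unscorable only under the source as described.
- The plan argues for difference scores. Replacing them in the main analysis would be a trade-off, not a correction.

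A reader might infer that exclusion is driven by arm. The documents do not support that. Students in care at launch began services before the intervention existed, so Partnership could not have changed their start dates. Only starts from 2019-20 onward could be influenced. A student starting in quarter 1 of 6th grade has had less than one quarter of exposure, and the Conceptual Framework's prediction of timelier services says nothing about that quarter.

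A reader might also put a total on the loss, using (1−s)/12 + s×f, where s is the share already in treatment and f the fraction of them without a pre-quarter. With s = .30, f = 0 gives .70/12 = 5.8% and f = .75 gives .058 + .225 = 28.3%. The documents give neither s nor f, and fractions for September 2019 do not carry over to later enrollees. No total can be supported.

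The objection leaves the gap itself standing: an outcome that needs a quarter the described records do not hold, with no rule for that case.

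**Conclusion.** The concern holds for one analysis, the Tier 3 academic change score. Students who start in quarter 1 of 6th grade have no pre-score under the plan as written. Nor do students already in treatment whose services began in elementary school or before quarter 2 of 2018-19. The first group is about 8% of new starts, assuming even starts and records through 2022-23. The second cannot be sized from the documents, although the Recruitment Plan expects it to raise early enrolment. The cost in precision is small: the MDES moves from .29 to about .32 even at 50% loss, given an ICC chosen to match the stated figure. What matters is that the baseline is undefined for a selected group. A difference between arms in who is excluded remains a possibility, limited to students whose start date the intervention could influence. Separately, the three years of record collection conflict with the four-year intervention period given elsewhere in Measures and Measurement Plan and in the Recruitment Plan.

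**What to change.** 1. In Measures and Measurement Plan and the Aim 2 paragraph, extend the record request for consented Tier 3 students to the quarter before services wherever the same district holds it (5th grade, 2017-18). Each state has one district.
2. Keep the difference score as the main analysis. Add a sensitivity analysis that retains students with no pre-quarter: post-service quarter as the outcome, pre-service value as a covariate, multiple imputation or a missing-baseline indicator, and a grade term. The indicator version is safest if missingness does not depend on arm, which item 3 helps to judge.
3. Report by arm the number of students without a pre-service quarter.
4. Reconcile the three years of record collection with the four-year intervention period.

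The cost is an added set of record fields, one further model and some plan wording, with no new visits or participants. It is not free. The plan describes de-identified records from study schools, so linked records from elementary schools may need new permissions, and 5th-grade marks may be on a different scale. Where permission is refused, items 2 and 3 still apply.

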**D. Study Design/Approach.** The study will involve 22 middle schools (12 in SC, 10 in MD) in a cluster-RCT, with all schools receiving the Wellness intervention and half of the schools (6 in SC, 5 in MD) randomized to receive enhanced intervention including the two SEs (Partnership). Stratified random assignment of schools to the Wellness Group or the Partnership Group will be conducted. We will then use validated procedures (23, 24) to further stratify schools within each state. We will construct a composite inflate-suppress score derived from school data on rurality, average number of students per grade, percent white, percent receiving free/assisted lunch, and average school test performance. Rurality within the two study sites will be operationalized by using a federally developed classification system used by The US Census Bureau (i.e., a 9-point, "Rural-Urban Continuum"). The coding scheme will distinguish three metro county categories based on population size, and six non-metro county categories based on degree of urbanization, as well as adjacency to other areas and metro proximity. Per operationalization of rurality in the federally-based coding continuum, we can confirm that the SC study sites contain county classifications of rural and suburban, while the MD site is exclusively urban. We will separate this composite into three strata and randomly assign schools from these strata to receive either the Wellness Group or the Partnership Group.

In the 5-year longitudinal design, Year 1 will involve administrative start up, collection of pre-assessments and intervention launch; Years 1-4 will involve intervention versus comparison while participants are in 6th through 8th grades. Year 5 will involve analyses and dissemination. A comprehensive implementation manual will guide the study and will be updated and improved regularly through active guidance of a Stakeholder Advisory Board (SAB, see Tables 3 and 4 in Appendix). The SAB will provide significant input as this manual is developed during the study start-up period from January through July, 2019, and progressively improved through study duration (see Gantt chart in Figure 1 of the Appendix for a review of all study activities in time).

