*Aim 1: Evaluate the impact of the Partnership enhancements in increasing the number of students and families receiving services and expressing satisfaction with them.* For this primary aim, and per experiences from prior RCTs (18,19), as mentioned, we will collect data for each student on the number of sessions conducted by the SBH clinician in categories of assessment; individual, group and family therapy; case management; and teacher consultation. In addition, during the COVID-19 school closure period we will document which students receive any of these services through telehealth, and will document this form of service received. This will enable coding of overall productivity, for types of services, and for family involvement in care. To measure satisfaction with services, at the three month or case closure assessment points, we will collect the Client Satisfaction Questionnaire-8 (CSQ-8) from students and parents. The CSQ-8 is a brief, widely used 8-item measure for use with youth aged 11 and older and adults (50).

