**Analytic Plan.** The proposed project is a cluster-randomized controlled trial (J=22 schools; 11 per treatment arm) comparing the efficacy of Wellness vs. Partnership services. As a general analytic plan, we will use hierarchical linear modeling (HLM) to evaluate the project aims. Specifically, we will use two-level HLM models to account for students being nested within schools. Though one might conceptualize this proposal as a three-level model (i.e., students nested within schools, and schools nested within sites), it would be neither feasible nor recommended to model site as a multilevel variable given there are only two sites in the design (56). In line with best practice, we will integrate site (i.e., SC vs. MD) as a covariate in the statistical models to contain any potential effects of this variable. Based on prior research conducted by the team, we expect intraclass correlations (ICCs) to warrant the incorporation of random intercepts to account for violations of independence. We will also test independence assumptions for the treatment parameters to determine how sensitive treatment effects are to potential violations of independence, and will include random slopes to account for nested treatment effects if ICCs exceed .01. For transparency, we will report both fixed and random effects (i.e. intercepts and slopes) of the model. Additionally, we will iteratively subset the model using a k-1 sensitivity analysis to determine the influence of individual sites on parameter estimates. We will estimate statistical models using full information maximum likelihood to accommodate any missing data (57). We will use maximum likelihood with robust standard errors to estimate models that include the Zero Inflated Poisson link function for count

PRINCIPAL INVESTIGATOR: [name]

outcomes (e.g. absences, referrals). This general analytic framework will be used in aims 1 and 2. Details, exceptions, and modifications to it are discussed below.

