*Model modifications for students receiving tier 3 services.* To evaluate the effects of the enhanced treatment on students who receive tier 3 clinical services, and to accommodate the fact that there will be a rolling admission into clinical services, the treatment parameter will be interacted with a dosage parameter measuring each individual student's weeks of treatment received. This interaction term will provide a treatment effect estimate that is calibrated by dosage, as measured by weeks of treatment received. Because we will use an active treatment, we will be able to detect treatment-by-dosage differences between the enhanced and control treatments. To accommodate the possibility that random assignment does not create exactly equal groups with K=22, and to provide interpretable estimates of change in response to the intervention, we will use difference scores as the dependent variable unit of analysis for students receiving tier 3 clinical services. This will facilitate the direct examination of how services received over time influences youth change. The null hypothesis associated with change scores is that baseline differences remain constant and there would thus be no mean change across measurement occasions. Rogosa and colleagues (58-60) highlight the utility of using difference scores to evaluate pretest-posttest change in similar studies, indicating that previous work critical of this approach has been misleading in that it focused on several restrictive assumptions including high correlations of pretest and posttest measures as well as equal variances across measures over time. Given our previous research, outcomes, and statistical model, we believe that difference scores are the appropriate dependent variable.

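### Schools are randomised from composite-score strata but the outcome models name only site, which may forgo precision in main-effect models without a baseline; any adjustment needs a 22-school correction

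*Combined protocol and SAP*

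**What the plan says.** Section D, Study Design/Approach, builds a school score from rurality, grade size, racial composition, subsidised-lunch share and test performance. It is used to "further stratify schools within each state", and then: "We will separate this composite into three strata and randomly assign schools from these strata". The same section notes that "we can confirm that the SC study sites contain county classifications of rural and suburban, while the MD site is exclusively urban".

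The Analytic Plan sets a two-level model with random school intercepts for Aims 1 and 2. Its only named design covariate is site: "we will integrate site (i.e., SC vs. MD) as a covariate in the statistical models to contain any potential effects of this variable". On estimation: "We will estimate statistical models using full information maximum likelihood to accommodate any missing data". No small-sample method or reference distribution is given. Count outcomes use a zero-inflated Poisson model with robust standard errors.

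Power considerations assumes that pre-test covariates explain 30% of variance, but does not list them. Tier 3 outcomes are analysed as difference scores, and "the treatment parameter will be interacted with a dosage parameter" for weeks of treatment. For satisfaction, "at the three month or case closure assessment points, we will collect the Client Satisfaction Questionnaire-8 (CSQ-8) from students and parents". For Aim 2a, prior-year records exist ("School-wide academic record data will be collected once annually for the academic year prior to study start (2018-19"), but no model names them as a covariate. Under Training and experience of recruitment personnel, two schools joined in Year 3, one per condition; their stratum and assignment method are not described.

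**The concern.** Stratified assignment balances the arms on the composite, so whatever the composite predicts is already removed from the true variance of the arm difference. A model that omits the composite still counts that variance as school-level error. With only 22 schools, school-level error dominates the standard error, so the design may buy precision that the analysis does not use. Difference scores deal with stable school differences in Tier 3 change outcomes. They cannot help an outcome first measured after treatment starts, such as the CSQ-8 or the Aim 1 session counts, and they are not prescribed for the school-wide Aim 2a records.

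The obvious remedy of simply adding strata terms has its own hazard. Under uncorrected maximum likelihood, each added school-level term makes the variance estimate more optimistic.

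**Working it through.** **1. The plan's own figure.** MDES = (t(.975, df) + t(.80, df)) × √[4ρ(1−R²)/J + 4(1−ρ)(1−R²)/N]. From the plan: J = 22, N = 1225, R² = .30, power 80%. The ICC ρ, alpha and the level at which R² applies are not stated. I assume two-sided 5%, R² at both levels and df = 20, and solve for ρ. Both stated values (.29 at N = 1225, .28 at N = 1400) follow for ρ of about .057 to .059. At ρ = .058:
- N = 1225: 2.946 × √(.00738 + .00215) = .288
- N = 1400: 2.946 × √(.00738 + .00188) = .284

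With R² at one level only, ρ would be .049–.052 (school) or .040–.041 (student). An ICC of .06 is therefore a fair illustration, not a figure from the plan.

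**2. How much too wide is the site-only standard error?** Let q be the share of remaining between-school variance that the strata explain (assumed). With no pretest and n = 1225/22 = 55.7 per school, a school mean has variance V = .06 + .94/55.7 = .0769. Balanced strata leave V − .06q in the arm difference, while the site-only model estimates roughly V. The ratio √[V/(V − .06q)] is:
- q = 10%: √(.0769/.0709) = 1.04
- q = 20%: √(.0769/.0649) = 1.09
- q = 30%: √(.0769/.0589) = 1.14

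Simulation on school means gives 5%, 9% and 15%. It assumes equal school sizes, MD strata of 4/2/4 schools, SC 4/4/4, and half of each stratum per arm.

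**3. What fitting the strata gains** (simulation, main effect, no pretest, all 1225 respond, t reference, two stratum terms):

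| q | MDES, site only | MDES, strata | Change | Power at d = .29 |
|---|---|---|---|---|
| 10% | .345 | .337 | −2% | 65% to 67% |
| 20% | .343 | .323 | −6% | 65% to 71% |
| 30% | .340 | .307 | −10% | 66% to 75% |

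At q = 20–30% the cut is 4–6% at ICC .02 and 6–10% at ICC .10. The formula in step 1 gives a larger cut at q = 30% (.345 to .304 at ρ = .058), because it does not credit the site-only analysis with the variance that stratification already removed.

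**4. Cost if q = 0.** The multiplier t(.975) + t(.80) is 2.954 at 19 df (site only), 2.963 at 18, 2.973 at 17 and 2.998 at 15. The rises are 0.3%, 0.6% and 1.5%. Simulation puts the loss for one or two terms at 0.5 to 1 power point (MDES +0.6% to +1.1%).

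**5. Uncorrected maximum likelihood.** Dividing the residual sum of squares by 22 instead of df shrinks the standard error by √(df/22). With a normal reference (assumed) and q = 0, type I error is P(|t(df)| > 1.96 × √(df/22)):
- site only, 19 df: cut-off 1.821, 8.4%
- plus one composite term, 18 df: 1.773, 9.3%
- plus two stratum terms, 17 df: 1.723, 10.3%
- six site-by-stratum cells, 15 df: 1.618, 12.6%

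For the site-only model the two errors offset. At R² = .30, simulated type I error falls from 8.4% at q = 0 to 6.1% at 20% and 5.0% at 30%. With a t reference it is 4.9%, 3.4% and 2.6%.

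**6. Other outcomes.** For continuous Aim 2a outcomes (600 students per school, ICC .10 assumed), the composite alone cuts the MDES by 7–13% at q = 20–30%. The school's 2018-19 mean alone cuts it by about 9%, 24% or 51% at baseline correlations of .5, .7 or .9 (assumed). Adding the composite to that mean changes it by only −5% to +1%. For a Tier 3 arm-by-weeks term, the standard error changes by under 1% for q up to 30%. If the composite shifts level equally before and after treatment, q for difference scores is 0. Count models were not computed.

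**The case against.** Several points on the other side stand.
- Site carries part of the composite, since Maryland is wholly urban, so the remaining share may be small. No ICC or q is documented, and every gain above is conditional on them.
- The CSQ-8 is collected in the Tier 3 stream. If the Tier 3 dosage interaction governs it, the gain nearly vanishes. It holds only if the main-effect (ITT) model does, and the plan does not say which applies.
- Strata formed within state need four terms, not two. If the stratum pattern differs by state, two common terms can even lose: at q = 30%, power at d = .29 was 65% site-only, 62% with two terms and 74% with six cells.
- REML with Kenward-Roger is a linear-model method and does not fit the zero-inflated Poisson models. The plan also chose full information maximum likelihood to handle missing data. REML still uses all available outcomes, but missing student-level covariates would need their own provision.
- Balance within strata is documented for at most 20 of the 22 schools.

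A reader might infer that Aim 1 satisfaction is the main casualty. The figures do not support that: the Aim 2a cut is at least as large when the 2018-19 mean is not adjusted for, and Aim 1 session counts have no baseline either.

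**Conclusion.** The mismatch between randomisation and model is plain in the text, and the point is worth considering. It concerns precision. A reader might infer that omitting the strata biases the treatment effect or inflates type I error. It does neither: under a school-based t reference the omission makes the test conservative. Nor can one infer that the planned test is conservative as it stands, because uncorrected maximum likelihood pushes the other way, and which effect prevails depends on q and on a reference distribution that the plan does not state.

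The exposure lies in main-effect models for outcomes without a baseline or difference score: Aim 1 satisfaction, Aim 1 services received (size not computed), and Aim 2a unless the 2018-19 school mean is adjusted for. Little or no gain is expected for Tier 3 difference scores or an arm-by-weeks term. The 6–10% cut in MDES rests on the assumed ICC of .06, q of 20–30%, no pretest, equal school sizes and balance within strata. The small-sample point holds even if the composite predicts nothing.

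**What to change.** In the Analytic Plan:
- For continuous main-effect models, add beside site either the randomisation composite as one continuous school-level term (18 df) or the strata as actually used (17 df if common to both states, 15 df if formed within state).
- In the same step, specify REML with Kenward-Roger or Satterthwaite school-based degrees of freedom. Do not add strata under uncorrected maximum likelihood.
- For Aim 2a, adjust first for the school's 2018-19 mean of the same outcome; the composite is then optional.
- For count models, use a small-sample method suited to them, for example a school-level t test or a permutation test within strata.
- State whether the main-effect or the dosage-interaction model governs the CSQ-8, and list the pre-test covariates.
- Record the composite value, stratum and assignment method for the two Year 3 schools.

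This takes a few sentences, plus composite and 2018-19 values for the two added schools, which the documents do not show as held. The price of a composite that proves useless is the small loss in step 4, slightly more with four stratum terms. The correction raises the site-only main-effect MDES from .265 to .292 at ICC .06 and R² = .30; that is what holding type I error at 5% costs.
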